7.2 Setting

The proposed setting for this study will be within seven European countries (Belgium [general practice EHR], Netherlands [general practice EHR], Germany [general practice EHR], France [general practice EHR], Italy [general practice EHR], Spain [general practice EHR, hospital EHR], and the United Kingdom [general practice EHR]).

The study will be conducted using data from multiple real-world data (RWD) sources previously mapped to the OMOP CDM in collaboration with the OHDSI and European Health Data and Evidence Network (EHDEN) initiatives.

Each cohort is defined in a separate setting (either hospital or primary care) based on the data source type and will be described at diagnosis of diagCOVID-19 or labCOVID-19 accordingly. The follow up will take place in the same setting and switch of setting (hospitalization for ambulatory cohorts or discharge for hospital cohorts) during follow up will be captured as an outcome.

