7.2.3 Follow-up

Two index date definitions will be applied as appropriate for each objective.

- Diagnosis index date is defined as a positive PCR test for SARS-CoV-2 (labCOVID-19) or a confirmed COVID-19 diagnosis(diagCOVID-19) whichever is the earliest.
- Treatment index date is defined as start of first systemic glucocorticoid treatment episode specifically for the treatment of COVID-19, irrespective of whether the patient is a prevalent or naïve user.

Follow up for all patients will begin from the index date until they experience the outcome of interest (endpoint, depending on the objective) or until cohort exit (date of censoring). The patients will be followed up for maximum 90 days or until censoring occurs, censoring criteria are:

- death
- patient exit (deregister) from a contributing data provider (GP practice)
- end of the database's data collection
- end of study period (latest data cut-off)

The lookback window for evaluating risk factors, medical history is 365 days and will be applied only to outpatient cohorts.

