SIDIAP is collected from EHR records of patients receiving primary care delivered through Primary Care Teams (PCT), consisting of GPs, nurses and non-clinical staff. The Catalan Health Institute manages 286 out of 370 such PCT with a coverage of 5.6M patients, out of 7.8M people in the Catalan population (74%). The database started to collect data in 2006. The mean follow-up is 10 years. The observation period for a patient can be the start of the database (2006), or when a person is assigned to a Catalan Health Institute primary care centre. Date of exit can be when a person is transferred-out to a primary care centre that does not pertain to the Catalan Health Institute, or date of death, or date of end of follow-up in the database. Drug information is available from prescriptions and from dispensing records in pharmacies. Drugs not prescribed in the GP setting might be underreported; and disease diagnoses made at specialist care settings are not included. Studies using SIDIAP data require previous approval by both a Scientific and an Ethics Committee (9).

Hospital de Madrid (HM) Hospitales (Spain)

Hospital de Madrid (HM) Hospitales data are made available through partnership with SIDIAP. The HM Hospitales database covers in-patient care delivered across a network of private hospitals in Spain. HM Hospitales covers more than 17M patients, out of whom a subset will be catalogued and followed for acute care delivered for suspected COVID-19 onset. This database covers more than 2300 confirmed COVID-19 cases and all in-patient hospital care, including the data of admission, conditions, procedures and medicines dispensed in hospital, date of discharge, and date of known death or date of end of follow-up in the database. Studies using HM Hospitales data require review and approval from data custodians at SIDIAP authorised to execute observational network analyses. The number of newly diagnosed patients in each database per month since the outbreak of COVID-19 can be derived from the databases.

None of the databases, except SIDIAP have linkage between primary and secondary care setting.

A database profiling, describing a range of variables in terms of data quality and completeness, as well as attrition tables for COVID-19 populations can be found at the following link:

https://dqdashboard.iqvia.com/ema_report1/.

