If exposure to glucocorticoids as second or third treatment occurs very often, a large proportion of patients will be censored, leading to limited data to assess the outcomes of interest.

Mitigation – an ITT sensitivity analysis is proposed in case censoring is very large (>70%)

7.9.2 **Databases related limitations**

Linkage between primary and secondary care

Seven out of eight databases will not have linkage between primary and secondary setting, and a consequence of this is that patient follow up time will be fragmented. Especially in the hospital setting, the access to medical history of the patient is limited and the patients who had prior exposure of glucocorticoids in primary care risk to be misclassified as naïve users.

Primary care databases

Severe outcomes that lead to hospitalization are less likely to be captured., although hospitalization is captured in some of the primary care databases.

If patients are free to change general practitioners and they are not tracked across different GPs or if they are treated. In private practice, their exposure will be underestimated and the follow up will be fragmented.

As the hospital and ambulatory settings are not linked, patients who had prior exposure of glucocorticoids in hospitals will be misclassified as naïve users.

Hospital setting databases

As the lookback period in the hospital setting is in general absent or reduced, there will be an under-ascertainment of baseline comorbidities.

Mortality data

The mortality information (vital status) is under-captured in some data sources. Three of them, DA Germany, LPD France and LPD Italy do not record vital status at all. For SIDIAP, the vital status comes from a regional mortality register while for HM Hospitales, the vital status comes directly from hospital records. For IMRD UK and IPCI, the vitals status information comes from GP recording.

Section 8.0 Protection of Human Subjects

For this study, participants from various EU member states will process personal data from individuals which is collected in national/regional electronic health record databases. Due to the sensitive nature of this personal medical data, it is important to be fully aware of ethical and regulatory aspects and to strive to take all reasonable measures to ensure compliance with ethical and regulatory issues on privacy.

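### Section 7.2.3 does not end follow-up at admission or discharge, so unlinked databases count person-time and no-glucocorticoid status that they cannot observe

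*Protocol*

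**What the plan says.** Section 7.2.3 fixes the end of follow-up: "The patients will be followed up for maximum 90 days or until censoring occurs, censoring criteria are" death, deregistration from the GP practice, end of the database's data collection and end of the study period. Otherwise follow-up stops only at the outcome under analysis. Section 7.2 says that follow-up takes place in the same setting and that "switch of setting (hospitalization for ambulatory cohorts or discharge for hospital cohorts) during follow up will be captured as an outcome".

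On what the data can show, Section 7.4 says "None of the databases, except SIDIAP have linkage between primary and secondary care setting". Section 7.9.2 adds, for primary care databases, "Severe outcomes that lead to hospitalization are less likely to be captured", and notes that hospitalization is captured in only some of them. HM Hospitales is described in Section 7.4 as covering in-patient care.

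Sections 7.3.2.3 and 7.7.4 use on-treatment person-time and censor patients who switch treatment. Section 7.7.8 adds an intention-to-treat analysis on all observed person-time if more than 70% are censored for switching.

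**The concern.** A change of setting ends follow-up only when admission or discharge is itself the outcome analysed. For adverse events, VTE/PE, DIC and drug use, the rules as written leave the patient at risk after the database has lost sight of the setting the patient moved to.

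Two things are at stake. In the hospital cohorts, time after discharge enters the denominator while events in that time cannot enter the numerator. In the unlinked GP databases, a glucocorticoid given in hospital is not recorded and so cannot trigger switch censoring. The patient stays with other treatments only or with no specific treatment, and may look like a non-initiator under the primary objective. Section 7.9.1 says glucocorticoids are indicated in severe cases only, so exposure is lost where it is most likely to occur.

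**Working it through.** The protocol gives no rate, stay length or admission share to reproduce. The figures below are illustrations on stated assumptions.

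**1. What the rules do.** Setting 7.2.3 beside 7.2: the only patient-level exits are death and GP deregistration, and the second cannot apply in a hospital database. Section 7.4 lists the HM Hospitales discharge date separately from the date of end of follow-up in the database, so the two are not stated to coincide.

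**2. How far hospital follow-up can run.** Table 1 locks HM Hospitales in April 2020. With a lock between 1 and 30 April, a full 90 days needs a diagnosis by 2 to 31 January 2020. A patient diagnosed on 1 March has at most 31 to 60 days. So 30 and 60 days are the relevant horizons, and 30 days is also the horizon of the meta-analysis in Section 7.7.7.

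**3. Hospital dilution.** Let L be the in-hospital days after index (assumed 7 to 21) and T the counted follow-up, with a constant low hazard in hospital and no event seen after discharge. Observed rate / in-hospital rate = L/T.
- T = 30: 7/30 = 0.23 to 21/30 = 0.70.
- T = 60: 7/60 = 0.12 to 21/60 = 0.35.

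This applies where person-time runs past discharge: chiefly the group with no specific treatment, which has no treatment end, and every group in the intention-to-treat analysis.

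**4. Ambulatory misclassification.** Let h be the share admitted. Section 5.0 reports progression to pneumonia and ARDS in 10-20%, used here as a proxy and widened to 5-20%. Let g be the share of admitted patients given glucocorticoids (assumed 20-80%). The share of initially untreated patients wrongly kept as without glucocorticoids is h × g: 0.05 × 0.20 = 1% to 0.20 × 0.80 = 16%.

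**5. Ambulatory person-time.** With a stay s of 7 to 21 days, the unseen share is h × s / T.
- T = 90: 0.05 × 7/90 = 0.4% to 0.20 × 21/90 = 4.7%.
- T = 30: 0.05 × 7/30 = 1.2% to 0.20 × 21/30 = 14%.

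In the ambulatory cohorts the diluted denominator is thus minor; missed exposure and missed in-hospital events matter more.

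**The case against.** The strongest reply is that follow-up may already stop near the switch. Section 7.2 confines it to one setting, and Section 7.4 bounds observation at the last consultation in four databases (LPD Belgium, LPD France, LPD Italy and DA Germany). This stands in part: an admitted patient who never consults again stops accruing time there. It does not help if the patient consults after discharge, because the stay then lies inside observation time. Nor does it cover IMRD UK, IPCI or HM Hospitales.

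Second, treated groups use on-treatment time, so the dilution does not reach them in the main analysis. That stands and limits the hospital figures to the groups named above.

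Third, Section 7.7.4 plans cause-specific models and Section 7.9.2 discloses the gap: "Seven out of eight databases will not have linkage between primary and secondary setting". Neither repairs it. The competing events are not named, and crude rates and proportions are unaffected. The misclassification that 7.9.2 describes concerns prior exposure (naïve or prevalent), not the treatment group during follow-up.

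Fourth, comparisons between groups are out of scope, so unequal dilution matters less. True, but each group's own rate is a stated result.

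Fifth, whether non-initiators enter the Kaplan-Meier analysis in Section 7.7.2 is unclear, because it is stratified by route and a non-initiator has none. Hence only the claim that they may appear as non-initiators.

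A reader might also infer more than the documents support:
- **A nine-fold understatement at 90 days** (90/10 for a 10-day stay). The April 2020 lock puts this out of reach for nearly all hospital patients.
- **83 of 90 days (92%) unseen** for a patient admitted on day 7. GP prescribing is visible again after discharge; a 10-day stay hides 10/90 = 11%.
- **No events seen at all after a switch.** Section 7.9.2 says less likely, not never, and adds: "For IMRD UK and IPCI, the vitals status information comes from GP recording". SIDIAP is linked and outside the problem.

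**Conclusion.** The point holds in limited form. As written, Section 7.2.3 lets follow-up continue past a change of setting in seven of eight databases, and no other rule in the protocol corrects this. The largest numerical effect is in HM Hospitales, for groups whose person-time continues after discharge: the rate falls to 0.23-0.70 of the in-hospital rate at 30 days and 0.12-0.35 at 60. In the unlinked GP databases the main harm is misclassified exposure in 1-16% of initially untreated patients, with little distortion of person-time.

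All these ranges rest on assumed stays, admission shares and treatment shares, a constant hazard in hospital, and no capture of events after discharge. The hospital range also assumes that follow-up does run past discharge, which the text permits but does not state outright.

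**What to change.** Add to Section 7.2.3: in unlinked databases, for drug utilisation and for all outcomes except the switch itself and death, follow-up ends at discharge in the hospital cohorts and at recorded admission in the ambulatory cohorts of databases that record hospitalization. In Section 7.7.4, name the switch as a competing event. This is needed because admission marks deterioration, and censoring at it is informative. Report death after a switch only where the source of vital status covers that period. State that the rates describe time in the observed setting, and flag databases without admission records as not correctable on this point.

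For discharge, and for admission where it is recorded, the cost is a short amendment and one more end date in the query, since both events are already outcomes in Section 7.3.4. The price is less person-time and no estimate of in-hospital events for ambulatory patients. The change recovers no event or drug given in hospital; it only stops unobserved time from being counted as observed. It should be settled before the final extraction, due by 1 February 2021 at the latest.

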7.2.4 Subgroups

The following subgroups will be used to stratify the descriptive tables in Primary objective 1 and secondary objective 1-3. These are a mix of contraindications (e.g. heart failure, myocardial infarction, ischaemic stroke, hypertension, diabetes) and underrepresented groups in clinical trials (e.g. renal

impairment, hepatic impairment) as well as conditions for which glucocorticoids are indicated (COPD and asthma).

Comorbidities

- Cardiovascular diseases¹ (e.g., hypertension, arrhythmia, valve disorders, stroke, acute myocardial infarction)
- Type 2 diabetes mellitus
- Respiratory diseases: asthma, COPD
- Renal impairment
- Hepatic impairment
- Autoimmune diseases (e.g., type 1 diabetes mellitus, rheumatoid arthritis, psoriasis, psoriatic arthritis, multiple sclerosis, systemic lupus erythematosus, Addison's, Graves, Sjogrens, Hashimoto, myasthenia gravis, autoimmune vasculitis, pernicious anaemia, celiac disease, scleroderma, sarcoid, ulcerative colitis, Crohn disease)
- Starting dose of steroids: low dose and high dose (the threshold will be decided based on data distribution)

Speciality of the healthcare practitioner (GPs vs specialists) in databases that record this information

The subgroups are not mutually exclusive, and patients can contribute to more than one subgroup, The above subgroups will be used for descriptive purposes and will not be used for statistical comparisons.

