7.3.2.3 Operationalization of exposure metrics

Cumulative duration

For glucocorticoids used in COVID-19 indication

Exposure to a treatment will commence on the date of the first qualifying record, subject to satisfying all inclusion criteria listed in section 7.2.2. Each drug exposure record has a start date and inferred end date, which is either explicitly entered or derived from other available information, such as days' supply or refills. Duration of each episode will be calculated as end date minus start date or directly from days' supply variable, whatever available. For each patient, the cumulative duration of use will be calculated as the sum of the duration of treatment episodes.

Table 3 Calculation of duration of use and end of treatment across databases

	IPCI	UK IMRD	Germany DA	Belgium LPD	SIDIAP	France LPD
If days_supply is missing	Use amount and dose extracted from the sig	Use daily dosage along with prescribed quantity	Impute with the most frequent daily dosage or DDD at a therapy level	Use calculated quantity/units_per_day.	Use the quantity, daily dosage and DDD of each drug	Use the quantity and daily dosage of each drug
If still missing	Use the DDD and prescribed quantity	Impute most frequent daily dose at the drug level	-	-	-	-
If still missing	Use the modal duration in the database					

DDD= defined daily dose; sig - the directions ('signetur') on the drug prescription as recorded in the original prescription (and printed on the container) or dispensing record from the physician.

Daily dose

For glucocorticoids used in COVID-19 indication, the prescribed daily dose at initiation of glucocorticoid (treatment index date) will be recorded and categorized in low and high dose. The definition of low dose and high dose will use the cut off defined by WHO in their prospective meta-

analysis from REACT subgroup (16), namely: 15 mg/d of dexamethasone, 400 mg/d of hydrocortisone, and 1 mg/kg/d of methylprednisolone.

The current recommendation is to use 10 mg of dexamethasone for maximum 10 days, administered orally or intravenously. In case glucocorticoids other than dexamethasone are administered, their dose will be converted in prednisolone equivalents as described:

<https://emedicine.medscape.com/article/2172042-overview>

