Steroids often have adjusted dose regimens such that drug may be slowly increased or decreased over time and short acute treatment episodes are also possible. Such changes in dose over time will not be examined, however total cumulative dose will be examined in relation to outcomes of interest (see below).

Cumulative dose

For glucocorticoids used in COVID-19 indication, orally administered, if quantity is available, the formula to calculate the cumulative exposure in mg is described below:

$$Cumulative\ dose_{solid}[mg] = \sum_{all\ exposures} quantity \times amount_value [mg]$$

If the **quantity is missing**, the number of units per day for solid formulations are extracted. The cumulative exposure in mg can then be calculated using the following formula:

$$Cumulative\ dose_{solid}[mg] = \sum_{exposures} units\ per\ day \times amount_value [mg] \times duration$$

For intravenous administration (bolus administration), the dose administered each time will be counted.

$$Cumulative\ dose\ intravenous [mg] = \sum_{all\ exposures} amount_value [mg]$$

Exposure groups for incidence calculation (secondary objective 2 and 3)

For the incidence rates calculation, an on-treatment exposure will be considered with mutually exclusive groups to allow calculation of incidence rates.

Each person will be classified as belonging to one of the following mutually exclusive exposure groups at treatment index date following COVID-19 diagnosis:

- Use of systemic glucocorticoids without other treatments for COVID-19 (drug and respiratory support)
- Use of systemic glucocorticoids plus other treatments for COVID-19 (drug and respiratory support)
- Only other treatments and respiratory support with no systemic glucocorticoids

- No specific treatments for COVID-19 infection (other concomitant treatments for indications other than for COVID-19 are allowed)

A single prescription would be enough to consider the patient as exposed. See section 7.3.2.1 for description of 'other treatment for COVID-19' that are included.

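### The low/high starting-dose split is set by two conflicting rules (7.2.4 and 7.3.2.3), and the fixed rule does not work for all five study glucocorticoids

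*Protocol*

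**What the plan says.** Protocol 7.2.4 lists starting dose among the subgroups that stratify the descriptive tables of the primary objective and of secondary objectives 1-3. It describes the categories as "low dose and high dose (the threshold will be decided based on data distribution". It adds that the subgroups "will be used for descriptive purposes and will not be used for statistical comparisons".

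Protocol 7.3.2.3, under Daily dose, says that the daily dose prescribed at the treatment index date "will be recorded and categorized in low and high dose". It then says: "The definition of low dose and high dose will use the cut off defined by WHO". The values printed are "15 mg/d of dexamethasone, 400 mg/d of hydrocortisone, and 1 mg/kg/d of methylprednisolone". The next paragraph states: "The current recommendation is to use 10 mg of dexamethasone for maximum 10 days". On conversion it says: "In case glucocorticoids other than dexamethasone are administered, their dose will be converted in prednisolone equivalents", with a link to an external table.

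Under Cumulative dose, the same section introduces the oral calculation with "the formula to calculate the cumulative exposure in mg is described below". It gives two oral formulas, with and without a recorded quantity, and one intravenous formula. All three sum milligrams.

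Protocol 7.3.2.1 names five study drugs: dexamethasone, prednisone, prednisolone, methylprednisolone and hydrocortisone. Protocol 6.2 names daily dose at initiation and cumulative dose as variables of the primary objective. Protocol 7.7.2 summarises them by the four cohorts and by subgroup and mentions no split by drug.

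**The concern.** A programmer cannot follow both sections unless the data-driven threshold happens to equal the fixed one. The same patient can be low dose under one section and high dose under the other. Because 7.7 presents results separately for each country and database, a threshold read from the data could also give the label high dose a different meaning in each database.

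Following 7.3.2.3 alone does not settle the matter, because its rule cannot be applied as printed to every study drug. The plan also leaves doses on more than one scale: four drugs in prednisolone equivalents, dexamethasone in its own milligrams, and cumulative dose in unconverted milligrams throughout.

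At stake are the dose tables of the primary objective, the dose strata in the tables of secondary objective 1, and the stratum-specific crude incidence rates by subgroup that 7.7.4 plans for secondary objectives 2 and 3.

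**Working it through.** The plan states no figure to reproduce. The check sets the sections side by side.

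**1. Same variable, two rules.** Protocol 7.2.4 splits the starting dose into low and high at a threshold taken from the data. Protocol 7.3.2.3 splits the daily dose at the treatment index date, which is the starting dose, into low and high at external cut-offs. Section 3.0 dates both additions 16 November 2020.

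**2. Coverage of the fixed rule.**

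| Study drug (7.3.2.1) | Cut-off in 7.3.2.3 | Usable as printed? |
|---|---|---|
| Dexamethasone | 15 mg/d | Yes |
| Hydrocortisone | 400 mg/d | Yes |
| Methylprednisolone | 1 mg/kg/d | Only with body weight |
| Prednisone | none | No |
| Prednisolone | none | No |

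Drugs with a cut-off: 3 of 5. Without: 5 − 3 = 2. Usable without body weight: 3 − 1 = 2 of 5. Protocol 7.3.5 lists no weight variable and takes obesity from diagnosis codes; a body-weight concept appears only in the obesity code list of Appendix 1.

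**3. Does the conversion supply the missing cut-offs?** No threshold in prednisolone equivalents is stated. As an illustration, assume ratios that are not in the protocol: 5 mg prednisolone equals 0.75 mg dexamethasone (range 0.5 to 1.0), 20 mg hydrocortisone or 4 mg methylprednisolone. Prednisolone equivalent = dose × 5 / (mg equal to 5 mg prednisolone).

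- Dexamethasone: 15 × 5 / 0.75 = 100 mg/d (range 75 to 150).
- Hydrocortisone: 400 × 5 / 20 = 100 mg/d.
- Methylprednisolone at assumed weights of 50, 70, 80 and 100 kg: 62.5, 87.5, 100 and 125 mg/d.

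Under these assumptions the three printed limits do not reduce to one prednisolone figure for every patient, so the figure has to be chosen and written down.

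**4. Effect of the conflict on dexamethasone users.** Read the recommended 10 mg as a daily dose (an assumption, since the sentence does not say per day). Then 10 / 15 = 0.67, so a patient at that dose is low under 7.3.2.3. Under 7.2.4, a dexamethasone threshold other than 15 mg/d moves every user whose dose lies between that threshold and 15 mg/d.

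**5. Scale of the milligram sums.** The protocol's own cut-offs place 400 mg/d hydrocortisone and 15 mg/d dexamethasone on the same boundary: 400 / 15 = 26.7. Raw milligrams are therefore not a common scale across drugs. The ratio shows a difference in scale and is not an effect size. It matters only if a summary combines drugs, or if a cumulative sum runs over a patient who changes drug. Protocol 7.7.2 neither plans nor rules out either.

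**The case against.** The strongest reply is that 7.3.2.3 is the defining text. It is the section that operationalises exposure, and Section 3.0 describes its amendment as defining the dose categories, whereas the 7.2.4 amendment only adds the subgroup. The data-driven wording then looks like a leftover. That is a fair reading and supports keeping the fixed rule. It does not remove the contradiction, because 7.2.4 is current text and tells the analyst something else. A SAP that follows one section departs from the other.

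A second reply is that the linked table lets the printed cut-offs be converted, and that the resulting number is SAP detail. The dexamethasone and hydrocortisone limits could be converted. Someone would still have to decide which limit defines the prednisolone cut-off, and a per-kg limit gives no single number.

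A third reply is that dexamethasone needs no conversion for the low/high split, because it has its own cut-off. That stands. Leaving it out matters only for dose summarised across drugs.

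A reader might infer that the dose tables are bound to be distorted by drug mix. The documents do not support this. No section says that milligrams are pooled across drugs, type of glucocorticoid is a separate descriptive variable in 6.2, and switching to another glucocorticoid censors follow-up in the incidence analyses. A reader might also infer that a dose-outcome analysis is compromised. Protocol 7.3.2.3 does say that cumulative dose will be examined in relation to outcomes, but 7.7.4 specifies no such analysis.

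**Conclusion.** The point holds as a conflict between two operative rules, together with a fixed rule that lacks a cut-off for 2 of 5 drugs and needs an unlisted variable for a third. The scale problem, with dexamethasone left out of the conversion and cumulative dose unconverted, is conditional on combining drugs.

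The number of patients affected cannot be given, because the protocol states neither the drug mix nor the dose distribution. The impact is limited to descriptive dose tables and dose-stratified crude rates: 7.2.4 rules out statistical comparisons of subgroups, and the four exposure groups for incidence are not defined by dose. Dose results for a single drug in its own milligrams, and results on duration, route and timing, are unaffected. The conclusion rests on the text alone; the equivalence ratios, the body weights and the daily reading of 10 mg are used only for illustration.

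**What to change.** 1. In 7.2.4, delete the data-driven wording and refer to 7.3.2.3.
2. In 7.3.2.3, state one fixed prednisolone-equivalent cut-off for prednisone and prednisolone.
3. State how the methylprednisolone cut-off applies when weight is missing, for example through a fixed mg/d equivalent.
4. Either convert all five drugs, dexamethasone included, to prednisolone equivalents before summarising daily dose and before summing cumulative dose, or report both by drug.

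The cost is wording in two sections and, if conversion is chosen, one step in the code. No new data are needed if a fixed methylprednisolone equivalent is used, but that equivalent is approximate. The high-dose stratum may also be sparse among dexamethasone users treated at 10 mg/d. It is better to accept and report that sparsity than to let the threshold move with the data.
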